#### **4.4.2            Secondary Efficacy Endpoints**

The fixed-sequence testing procedure will be used ([Westfall and Krishen 2001](#)) to adjust for multiple statistical testing of the primary and key secondary efficacy endpoints, thereby controlling the overall type I error rate at a 2-sided significance level of 5%.

The following secondary endpoints will be tested in the *TP53* WT population in the following order provided the null hypothesis of the OS primary endpoint is rejected:

1. CR rate
2. EFS
3. OR (CR, CRp and CRi) rate
4. DOR (duration of CR)
5. Proportion of patients who received HSCT following CR
6. CR rate in mutation defined subgroup: FLT3
7. OS in mutation defined subgroup: FLT3
8. CR rate in mutation defined subgroup: IDH2
9. OS in mutation defined subgroup: IDH2
10. CR rate in mutation defined subgroup: IDH1
11. OS in mutation defined subgroup: IDH1

A given hypothesis in the list above will only be rejected once all previous hypotheses have been rejected at the 2-sided significance level 5%.

Response will be evaluated according to the HMRA criteria (see protocol section 4.5.8) as the best assessment of response over the induction cycle (cycle 1). The frequencies and percentages of patients assigned to each HMRA response category, that is, CR, CRp, CRi, non-responder (partial response [PR], stable disease [SD], resistant disease, relapsed disease, death in aplasia, and death from indeterminate cause), or not available (NA) will be summarized by treatment arm along with the 2-sided 95% CI according to the Pearson-Clopper method.

For the interim futility analysis patients with no response assessments will be considered as NA, unless they directly proceeded to HSCT after Cycle 1. These patients will be considered confirmed CR unless transplantation was clearly performed in relapse.

Proportions of CR as well as ORR (CR, CRp, and CRi) and HSCT will be compared between the two treatment groups using Cochran–Mantel–Haenszel test stratified by the randomization stratification factors. The effect of prognostic factors on these binary endpoints will be assessed in an exploratory analysis using logistic regression.

The time-to-event endpoints, EFS and DOR, will be analyzed using the same statistical methods as described for the primary OS analysis. If very few patients qualify for DOR analysis, only descriptive statistics of DOR will be given.

#### **4.4.3            Sensitivity Analyses:**

The following sensitivity analysis will be performed in the *TP53* WT population and all-patient ITT population:

- An unstratified log-rank test for OS
- Discontinuation of assessments or patient lost to follow up considered as an OS event
- An unstratified chi-squared test for CR

A check of the proportional hazards assumption for OS will be performed by plotting the log negative log of the estimated survivor function against log time.

The following sensitivity analysis for OS will be performed in the ITT population:

- A multivariate sensitivity analysis of OS in the ITT population using Cox proportional hazards multiple regression to assess the treatment effect after adjustment for *TP53* mutation status.

To assess the relevance of new treatment for AML against other long-term effects, OS in the *TP53* WT population will be alternatively defined with censoring at date of new treatment and analyzed using the same methods as for the primary OS endpoint

A sensitivity analysis of OS on the subset of patients *TP53* WT (i.e. not including those with retained functionality) will be performed.

To assess the relevance of HSCT against other long-term effects, OS in the *TP53* WT population will be alternatively defined with censoring at date of HSCT and analyzed using the same methods as for the primary OS endpoint.

The confounding effect of HSCT on OS will be assessed using a Cox multivariate regression including major covariates (e.g., prior HSCT, HCT-CI score, leukemia status, type of donor and transplant, engraftment status, conditioning therapy type, site). Only covariates that are significant at 0.15 level in the univariate analysis will then be included in a multivariate analysis, and backward selections at the 5% level will be performed to obtain the model.

Different definitions of EFS will be assessed in sensitivity analyses, in which EFS is defined as

- a) time from randomization to the date of treatment failure (failure to achieve CR, set as day 1), relapse from CR, or death from any cause, whichever comes first

- b) time from randomization to the date of treatment failure (failure to achieve CR, CRp or CRi, set as day of final response assessment), relapse (from CR, CRp or CRi) or death from any cause, whichever comes first
- c) time from randomization to the date of relapse from CR (for subjects who achieved CR) or death from any cause, whichever comes first
- d) the above definitions censoring at HSCT.

For time to event analysis the following sensitivity analyses will be performed:

- Patients who report a new treatment post-randomization for follow-up cancer therapy will be considered as having an event (OS and EFS for respective sensitivity analysis) at time of new treatment intake.
- Discontinuation of assessments or patient lost to follow up considered as an event (for OS, and EFS)

#### **4.4.4 Subgroup Analyses**

The effects of prognostic factors at baseline, as well as demographic and disease characteristics at baseline, on treatment comparisons for OS (in *TP53* WT ITT population) will be examined and assessed using Cox multivariate regression.

The estimated Kaplan-Meier OS event rates, as well as the HR estimated using an unstratified Cox regression model and 95% CI will be displayed by treatment arm for each level of the subgroup. The subgroup analysis results will be displayed using forest plots ([Lewis and Clarke 2001](#)) for stratification factors, the demographic and disease characteristics at baseline, including history of AML.

Descriptive statistics on disease and patient status as well as transplant procedure and engraftment use will be produced to support the analysis of confounding effect of HSCT on OS.

The study is not powered to detect a treatment difference in subgroups. Results from these analyses should be interpreted as exploratory.

#### **4.5 PHARMACODYNAMIC AND BIOMARKER ANALYSES**

Exploratory analyses might be performed on bone marrow and blood specimens to identify and/or evaluate the presence of PD biomarker and other biomarkers that might help predict patient subpopulations that are more likely to respond to idasanutlin + cytarabine.

The following PD and biomarker parameters will be presented in patient listings and descriptive summary statistics by treatment arm:

- Mic-1 protein levels in blood samples (analyzed by ELISA)

- *TP53* mutation status
- Rate of CRMRD (MRD response as per ELN guidelines) using multiparameter flow cytometry
- Baseline expression levels of a 4-gene signature will be analyzed by qRT-PCR from patient blood. The predictive or prognostic value of these markers will be analyzed at futility-interim analysis (gene signature) and at the time of primary analysis. These biomarker analyses are exploratory and are not part of the futility interim analysis assessment. However, the iDMC will make a recommendation based on the prognostic and potential value of these markers to inform the decision on how these markers will be further evaluated after the futility-interim analysis; see Section 6.4.4 of the iDMC Charter for further details.
- MDM2 protein expression in blasts may also be analyzed relative to patient outcomes at the end of study.

Details of the biomarker analyses will be described in a separate biomarker analysis plan.

#### **4.6 PHARMACOKINETIC ANALYSES**

Details of the PK analyses will be described in the Modeling and Simulation Analysis Plan. Results of this analysis will be reported separately.

#### **4.7 SAFETY ANALYSES**

The safety analysis population will be used for all safety analyses (Section 4.1.4).

##### **4.7.1 Exposure of Study Medication**

Study treatment exposure (idasanutlin+cytarabine and placebo+cytarabine) will be summarized using descriptive statistics (by treatment arm) for the following measures:

- Number of patients treated overall and by treatment cycle
- Number of days on treatment
- Study medication duration
- Number of treatment cycles started
- Number of doses received and missed doses
- Cumulative dose received
- Dose intensity
- Number and reasons for dose modification and discontinuation

##### **4.7.2 Adverse Events**

Coding of adverse events will be done using the most recent version of the Medical Dictionary for Regulatory Activities (MedDRA). All adverse events and

laboratory parameters will be assessed according to the National Cancer Institute Common Terminology Criteria for Adverse Event (NCI CTCAE) version 4.03 grading system.

All adverse events will be reported from the day of first study treatment. All adverse events will be displayed by body system (system organ class), NCI CTCAE grade, and relation to study treatment. All serious adverse events, Grade  $\geq 3$  adverse events, adverse events leading to death, adverse events leading to study treatment modification, adverse events leading to study treatment discontinuations, and adverse events leading to early study withdrawals will be summarized by treatment arm.

Deaths and reason for deaths reported during the study will be summarized by treatment arm. Deaths occurring within 30 and 60 days after randomization will also be summarized.

In the summary tables showing the overall incidence of adverse events, patients who experienced the same event on more than one occasion will be counted only once in the calculation of the event frequency. The adverse event with the most extreme intensity will be used for reporting.

Additional analyses will be performed by treatment arm based on the selected adverse events of special interest, which are defined in the study protocol, as well as based on any adverse event, which might require further investigation. Analyses of the time to onset of these adverse events will be performed. Time to adverse events will be listed. Patients without an adverse event will be censored at last date known to be alive.

In order to account for potential differences in the duration of adverse event reporting between treatment groups, an exploratory analysis of selected adverse events by duration of exposure might be performed based on adverse event rates adjusted for patient-years at risk when enough events are observed.

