## Follow-Up

Patients in CR/CRp/CRi after terminating study treatment will be followed for EFS, *DOR*, and *LFS*. HMRA will be performed monthly ( $\pm 5$  days) until disease progression/relapse is noted or until the patient moves to HSCT. Every 3 months HMRA will include assessment of bone marrow aspirate; in all other instances, HMRA will be based on peripheral blood counts only.

In the event of relapse, a HMRA based on a bone marrow aspirate is required. In addition, whole blood in EDTA for biomarker analysis should be obtained.

For patients who move to HSCT, an HMRA based on a bone marrow aspirate should be performed to document the bone marrow status prior to the start of conditioning therapy. The quantity of the bone marrow aspirate should also allow for exploratory biomarker analyses (MRD/Flow, EDTA, and Paxgene), and the hematopoietic cell transplantation-specific comorbidity index (HCT-CI) score (Sorrer et al. 2005; Sorror 2013) should be obtained to document the patient's health status prior to the start of conditioning therapy.

All patients will be followed every 3 months for study treatment-related serious adverse events, fatal adverse events, subsequent anti-cancer therapies, and survival status. Survival follow-up ends with death or end of study. Adverse events should be followed as outlined in Section 5.3.1 and Section 5.6. Please see [Appendix 1](#) for the schedule of follow-up assessments.

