### **5.3.1 Adverse Event Reporting Period**

Investigators will seek information on adverse events at each patient contact. All adverse events, whether reported by the patient or noted by study personnel, will be recorded in the patient’s medical record and on the Adverse Event eCRF.

**After informed consent has been obtained but prior to initiation of study drug**, only serious adverse events caused by a protocol-mandated intervention (e.g., invasive procedures such as biopsies, discontinuation of medications) should be reported (see Section 5.4.2 for instructions for reporting serious adverse events).

**After initiation of study drug until 56 days after the last dose of study drug**, all adverse events should be reported. Patients who, at 56 days after the last dose of study medication is administered, have an ongoing adverse event will be followed until the event resolves or the patient is lost to follow-up.

**After informed consent has been obtained until 6 months after the last dose of study medication is administered**, adverse events of special interest are reportable with the exception of hematological adverse events of special interest arising as a result of confirmed relapsed disease (see Section 5.2.3 for adverse event of special interest definition).

**After 56 days from the last dose of study drug until the end of the study**, the investigator should only report any serious adverse events that are believed to be related to the prior administration of study drug treatment or any fatal adverse events. Those should be reported on the eCRF Adverse Event page over the course of the study (see Section 5.6).

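### SAP 4.7.2 censors time-to-adverse-event analyses at the last date known alive, beyond the dates at which the protocol stops collecting most adverse events

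*SAP*

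**What the plan says.** SAP 4.7.2 plans additional analyses of AESIs and of any other adverse event that may need further investigation. It commits to time to onset: "Analyses of the time to onset of these adverse events will be performed". It says that the times will be listed, and then gives the censoring rule: "Patients without an adverse event will be censored at last date known to be alive". The next paragraph allows, as an optional exploratory analysis, rates adjusted for patient-years at risk, because the duration of adverse event reporting may differ between arms. It does not say when a patient's time at risk ends.

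Protocol 5.3.1 sets the collection periods:

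- All adverse events: "After initiation of study drug until 56 days after the last dose of study drug".
- AESIs: "After informed consent has been obtained until 6 months after the last dose of study medication is administered". A carve-out narrows this for patients who relapse, since the reporting duty applies "with the exception of hematological adverse events of special interest arising as a result of confirmed relapsed disease".
- Later than day 56 after dosing stops, and for as long as the trial runs, reporting narrows: sites "should only report any serious adverse events that are believed to be related to the prior administration of study drug treatment or any fatal" ones.

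Survival runs on a different clock. The Follow-Up part of Protocol 4.5.2 has all patients contacted every 3 months, and "Survival follow-up ends with death or end of study".

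**The concern.** A patient should count as at risk of an event only while that event could be recorded. Here the censoring date comes from survival contacts, which can continue for months or years after collection has stopped. A patient who receives Cycle 1 only takes the last dose on Day 5. General collection ends at about Day 61 (5 + 56) and AESI collection at about 6 months, yet the patient stays in the risk set as event-free until death or last contact.

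The SAP handles comparable endpoints differently. Time to deterioration in quality of life is censored at the last non-missing assessment (SAP 4.8.1), and leukemia-free survival at the last response assessment (SAP 2.2.4).

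At stake is the reading of the safety curves. A plateau with no data behind it would look like freedom from events, and incidence would be too low wherever some patients' windows have closed while others' are still open.

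**Working it through.** **Step 1. Reproduce the plan's survival model.** Inputs from Protocol 6.1 and 6.11.1: complete response (CR) probability 0.16 (control) and 0.323 (idasanutlin); half of complete responders are long-term survivors; control medians of 5.1 months (non-responders) and 7.5 months (short-term responders); hazard ratio 0.8 in both of those groups; exponential times.

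- Control: S(t) = 0.84·exp(−t·ln2/5.1) + 0.08·exp(−t·ln2/7.5) + 0.08. Median 5.96 months.
- Idasanutlin: S(t) = 0.677·exp(−0.8·t·ln2/5.1) + 0.1615·exp(−0.8·t·ln2/7.5) + 0.1615. Median 8.97 months.
- CR odds ratio: (0.323/0.677)/(0.16/0.84) = 2.50.
- Minimum detectable hazard ratio: exp(−1.96/√(275 × 2/9)) = 0.778, that is 6 to 7.71 months.
- Simulated power at 275 events with 374 patients: 85.0% with 41-month accrual.

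These match the stated 6 and 9 months, 2.5, 0.78 and 85%, so the model can be used to project follow-up.

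**Step 2. Time to last known alive.** With uniform accrual over 41 months, cut-off at 48 months (SAP 2.4: about 4 years) and dropout δ = −ln(0.95)/12 per month, the mean is ∫ S(t)·exp(−δt)·G(t) dt from 0 to 48. G(t) = 1 up to 7 months and (48 − t)/41 after that. The results are 8.4 months (control) and 11.3 months (idasanutlin).

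**Step 3. Part of that time inside the collection window.** The same integral is stopped at last dose + 56 days or + 6 months. The last dose is Day 5, plus two further cycles for responders who take three. The number of cycles and cycle lengths of 28 to 56 days are assumptions, so a range is shown (all times in months).

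| Responders' treatment | Arm | Mean to last alive | Inside 56-day window | Share after it | Inside AESI window | Share after it |
|---|---|---|---|---|---|---|
| 1 cycle | Control | 8.38 | 1.77 | 79% | 4.33 | 48% |
| 1 cycle | Idasanutlin | 11.27 | 1.84 | 84% | 4.78 | 58% |
| 3 cycles of 28 days | Control | 8.38 | 2.03 | 76% | 4.54 | 46% |
| 3 cycles of 28 days | Idasanutlin | 11.27 | 2.37 | 79% | 5.24 | 54% |
| 3 cycles of 56 days | Control | 8.38 | 2.27 | 73% | 4.73 | 44% |
| 3 cycles of 56 days | Idasanutlin | 11.27 | 2.86 | 75% | 5.65 | 50% |

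At the end of study (41 + 24 = 65 months) the shares are 77–82% (control) and 80–87% (idasanutlin) for the 56-day window, and 53–57% and 61–67% for AESIs.

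**Step 4. Effect on estimates.** As an illustration, assume the same constant event hazard of 0.05 per month in both arms and three 28-day cycles for responders.

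- *56-day window, Kaplan–Meier at 3 months.* True value 1 − exp(−0.15) = 13.9%. The SAP rule gives 10.4% (control) and 11.1% (idasanutlin). Censoring at window end gives 13.8% and 13.9%.
- *AESI window, Kaplan–Meier.* The two rules agree to 6 months (about 26%). At 9 months the SAP rule gives 28.3% and 29.2%, against 33.0% and 32.7% when censored at window end. The last window closes at about 8 months, so the curve should stop there.
- *Crude events per patient-month, if last-alive time were the denominator.* 56-day window: 0.0128 and 0.0111, ratio 0.87. AESI window: 0.0297 and 0.0256, ratio 0.86. Ending time at the window gives about 0.050 in both arms.
- *Cox hazard ratio (true value 1).* The SAP rule gives 1.11 for the 56-day window and about 1.02–1.03 for AESIs. Censoring at window end gives about 1.0 for both.
- *If every patient had one cycle only.* The 56-day Kaplan–Meier estimate is 9.5% in both arms under either rule, and the hazard ratios do not change.

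**The case against.** The strongest reply is that little follows in practice. SAP 4.7.2 names no test, hazard ratio or survival curve for onset. The main target is AESIs, whose window is 6 months, and most of these events would be expected early. Where all patients have the same window, no events are recorded after it, so Kaplan–Meier and Cox results are the same under either rule. The safety stopping criteria use proportions and 30-day deaths, and overall survival is untouched. The SAP also shows awareness of unequal reporting time through its exploratory rate analysis.

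Much of this limits the size of the problem, and it rules out several stronger readings that a reader might infer:

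- *That about 80% of all counted time is unobserved.* This fits the 56-day window only. For AESIs the share is about half at the final survival analysis, and below half in control.
- *That nothing is collected after the window.* Drug-related serious events and fatal events are reported to the end of the study, and for those the last-contact date is a proper censoring date.
- *That the bias favours idasanutlin.* This holds only for crude person-time rates under a survival benefit. In Kaplan–Meier and Cox analyses the small tilt runs the other way, because more idasanutlin patients respond and so may have longer windows.
- *That patient-years will run to the last-alive date.* The SAP does not say so; it leaves the end of time at risk undefined.

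The mismatch itself remains. The time-to-onset analyses are a commitment, the censoring rule is explicit, and the optional rate analysis does not alter it.

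**Conclusion.** The censoring rule is wrong as written and should be corrected. At the 48-month analysis it counts as event-free about 73–84% of time to last known alive for events with the 56-day window, and about 44–58% for AESIs, during which those events were not being collected. These shares rest on the plan's survival assumptions, 41-month accrual, and one to three cycles of 28 to 56 days for responders. The AESI shares take no account of the exclusion of hematological AESIs due to confirmed relapse, which would raise them.

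Cumulative incidence is understated once patients begin to pass their window. Any rate using last-alive time would be too low. The arms can be affected differently because survival and number of cycles differ, but the documents do not support a fixed direction: it depends on the summary used, and the difference would be small if survival and cycles were equal. The sizes in Step 4 depend on the assumed hazard and are illustrative. Early Cycle 1 estimates change little. The issue concerns secondary safety summaries, not the primary survival test.

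**What to change.** Replace the censoring sentence in SAP 4.7.2 with a rule specific to event type. Censor patients without the event at the earliest of death, last contact, data cut-off and the end of collection for that event:

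- adverse events in general: last dose + 56 days;
- AESIs: last dose + 6 months ("until 6 months after the last dose of study medication is administered"), or confirmed relapse if earlier for hematological AESIs;
- drug-related serious events and fatal events: no window cut, so follow-up to last contact is kept.

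Define patient-years at risk in the exploratory rate analysis with the same end date, and end any plotted curve where the last window closes.

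Also reconcile the protocol with itself. The adverse event footnote to the Post-Treatment Phase table in Appendix 1 limits some follow-up visits to treatment-related serious events and fatal events, while Sections 5.3.1 and 5.6 have AESIs reportable for 6 months after the last dose. Until these passages agree, the AESI window may not be applied in the same way at all sites.

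The cost is a short SAP change and one derived date per patient and event type, from dosing, relapse and contact dates already held. The footnote needs a clarification in the protocol.

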#### **4.7.3            Laboratory Data**

Laboratory data with values outside of the normal ranges will be identified. Laboratory values will be summarized by treatment arm and grade using the NCI-CTCAE version 4.03 grading system. Shift tables will be used to present the number and percentage of patients with values within, above, or below the normal range comparing baseline to subsequent assessments by treatment arm.

Nadir is defined as the lowest value observed in the interval between Cycle 1, Day 1 up to and including predose on Cycle 2, Day 1. If there is no Cycle 2, Day 1 value, and the interval between Cycle 1 Day 1 and Cycle 2 Day 1 is not definable then the latest value in Cycle 1 will be used to define the interval. If no

value is lower than baseline (i.e., Cycle 1, Day 1 cannot be the nadir), then the nadir does not exist, and the patient is excluded from the analysis.

For all patients summary statistics and boxplots for time to nadir (in days) will be produced by treatment arm, as well as Kaplan Meier for time to nadir starting on study drug first administration.

Time to recovery is defined as the time until the value crossed back up and over 100 for platelets and over the thresholds 0.5 or 1 for neutrophils after the interval between Cycle 1, Day 1 and the predose on Cycle 2, Day 1. If there is no Cycle 2, Day 1 value, then the latest value in Cycle 1 will be selected. Patients receiving a transfusion within 24 hours prior to the laboratory assessment selected will be excluded.

For responders only (CR, CRp, CRi), summary statistics and boxplots for time to recovery (in days) for both neutrophils and platelets will be produced by treatment arm, as well as Kaplan Meier for time to recovery starting on study drug first administration.

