##### **5.1.1.2 Cytopenias**

Cytopenias, including myelosuppression, are expected under the anti-leukemia treatment proposed, and the therapeutic effect is expected to be associated with toxicity on normal bone marrow progenitors. Bone marrow toxicity may manifest as cytopenias (i.e., pancytopenia, neutropenia, febrile neutropenia, thrombocytopenia, and anemia). In Study NP27872, which evaluated idasanutlin in patients with solid tumors, possible

exposure-dependent neutropenia and thrombocytopenia were observed; these events were reversible and able to be monitored. In leukemia patients, drug-induced myelosuppression is expected during idasanutlin treatment, and idasanutlin administered in combination with cytarabine may prolong the aplasia window. In Study NP28679, the time to platelet and neutrophil recovery were highly variable, and the mean time to recovery for platelet and leukocyte counts (Kaplan-Meier estimates) were 34 days in patients who responded to idasanutlin and cytarabine administered in combination.

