### **5.1.2.2 Myelosuppression**

For patients who are neutropenic and thrombocytopenic at baseline due to their underlying leukemia, elimination of leukemic blasts is essential for normal bone marrow recovery. Idasanutlin was associated with myelosuppression in Study NP28679, but normal bone marrow recovery was observed in patients showing a clinical response. Additive effects from idasanutlin administered in combination with cytarabine on normal bone marrow progenitors (including early progenitors) are possible.

In anticipation of a potential extended period of myelosuppression, the standard precautions for neutropenia, thrombocytopenia, and anemia will be used for patients in the trial. In this study, blood counts will be monitored closely throughout treatment (see [Appendix 1](#)). Administration of growth factors will be permitted for neutropenic sepsis according to local practice, and patients will be monitored and treated promptly should infection occur. Patients will be excluded from study participation if they are unwilling to

undergo supportive blood transfusion therapy. Please refer to [Appendix 14](#) for guidelines for hematological toxicity management.

Please note that events of febrile neutropenia Grade  $\geq 3$  and thrombocytopenia Grade  $\geq 3$  (if associated with hemorrhage or bleeding) are considered adverse events of special interest for idasanutlin (see Section [5.2.3](#)).

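### SAP 4.7.3 excludes patients whose counts never fall below baseline, so the by-arm time-to-nadir curve reaches 100% in both arms and cannot show whether falls are more common on one arm

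*SAP*

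**What the plan says.** SAP 4.7.3 takes the nadir as the lowest value from Cycle 1 Day 1 up to the predose sample on Cycle 2 Day 1. Where that end point is missing, the interval runs to the latest Cycle 1 value. The Day 1 value itself cannot be the nadir. Where nothing lower than baseline is seen, "then the nadir does not exist, and the patient is excluded from the analysis".

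The next paragraph sets out the outputs: "For all patients summary statistics and boxplots for time to nadir (in days) will be produced by treatment arm". It adds a Kaplan-Meier analysis of time to nadir from first study drug administration. No test is specified. Nothing says whether a patient without a fall is absent from the Kaplan-Meier analysis or censored in it, and no count of such patients by arm is planned.

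The same section plans two other laboratory outputs that do not require a fall: "Laboratory values will be summarized by treatment arm and grade using the NCI-CTCAE version 4.03 grading system", and "Shift tables will be used to present the number and percentage of patients with values within, above, or below the normal range", comparing baseline with later assessments. SAP 4.7 states that "The safety analysis population will be used for all safety analyses".

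**The concern.** Whether a count drops below its baseline is an outcome of treatment, and the rule uses it as the condition for entering the analysis. The sets compared are then no longer the treated arms but the subsets of each arm in which a fall occurred. If falls are more common on idasanutlin, a larger share of the placebo arm is removed, and the display hides that difference.

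The output concerns a named risk. Protocol 5.1.2.5 defines hematologic toxicity as a cytopenia that worsens after study medication starts, so the rule conditions on the event that the protocol itself treats as toxicity. Protocol 1.2.2.2 reports an apparent relationship between exposure and the Cycle 1 platelet nadir. A reader of the study report could take two curves that both reach 100% as evidence that all patients in both arms had a fall.

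**Working it through.** **No figure to reproduce.** The documents give no sample size, fall rate, test or power for the nadir analysis. The check is one of structure, followed by an illustration on assumed rates.

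**Structure.** In one arm, let n be the number of treated patients with a post-baseline Cycle 1 count, and p the share with at least one value below baseline.

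- The rule keeps n × p patients and removes n × (1 − p).
- Among those kept, the share with a fall is (n × p)/(n × p) = 100%, whatever p is.
- Every kept patient has a nadir day and none is censored. The Kaplan-Meier estimate is the product of (1 − d/r) over event days, where d is the number of events and r the number at risk. On the last nadir day d = r, so the estimate is zero and the cumulative curve is 100% in each arm.

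**Illustration.** Arm sizes are the approximate 293 and 147 of SAP 3.1. All patients are assumed to be treated and to have a post-baseline count. The fall rates are assumptions.

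| Assumed fall rate, idasanutlin vs placebo | Removed, idasanutlin | Removed, placebo | Difference in all treated | Displayed |
|---|---|---|---|---|
| 95% vs 90% | 293 × 0.05 ≈ 15 | 147 × 0.10 ≈ 15 | 5 points | 100% vs 100% |
| 95% vs 85% | 293 × 0.05 ≈ 15 | 147 × 0.15 ≈ 22 | 10 points | 100% vs 100% |
| 90% vs 75% | 293 × 0.10 ≈ 29 | 147 × 0.25 ≈ 37 | 15 points | 100% vs 100% |

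If patients with no fall were instead kept and censored at the end of a common interval, the curves would level off at the rates in the first column. The interval here varies between patients, so the plateau need not equal the simple proportion exactly. The count with no fall should therefore be reported as well.

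**The SAP's own practice elsewhere.** SAP 4.7.2 censors patients without the adverse event at the date last known alive. SAP 4.8.1 censors patients without an observed deterioration or improvement at their last assessment. The nadir rule departs from this without giving a reason.

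**What the other outputs can see.**

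- Shift tables classify values as within, above or below the normal range. A patient below normal at baseline who then falls further stays in the same category. Protocol 5.1.2.2 expects such patients: "For patients who are neutropenic and thrombocytopenic at baseline due to their underlying leukemia".
- The grade summary does not depend on a fall, but the SAP does not say that it is set against baseline grade.
- Adverse event tables cover Grade 3 or higher events and the events of special interest. The latter include febrile neutropenia of Grade 3 or higher and thrombocytopenia of Grade 3 or higher with bleeding (Protocol 5.2.3). Protocol 5.3.5.4 does not require a cytopenia attributed to the leukemia to be reported as an adverse event.

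**The case against.** The strongest reply has three parts.

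First, a patient with no low point has no day on which it occurred. Restricting boxplots and summary statistics in days to patients with a nadir is therefore a matter of definition. This stands. The objection is to the Kaplan-Meier handling and to the missing count, and the boxplots need only a label.

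Second, the sentence that announces the output for all patients need not contradict the exclusion. A later paragraph of SAP 4.7.3 restricts time to recovery to responders, and the contrast may simply be all patients versus responders. This is a fair reading. The two sentences need aligning, but they do not prove a contradiction.

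Third, myelosuppression is examined elsewhere, in grade summaries, shift tables and adverse event tables by arm. This also stands, subject to the gaps listed above. The limitation belongs to the nadir analysis and not to the whole safety plan. The protocol's remark that "idasanutlin administered in combination with cytarabine may prolong the aplasia window" concerns duration, which the SAP addresses through time to recovery, so it adds little here.

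Two stronger readings are tempting and are not supported.

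- A reader might infer that the rule removes the most cytopenic patients. It removes anyone without a fall, including patients with adequate counts that hold or rise. Patients near the floor may be over-represented, but the documents give no rates. In a simulation with assumed lognormal baselines (median neutrophils 0.8 and platelets 40 × 10⁹/L), large assumed falls and a lower floor, 85% of patients with baseline neutrophils under 0.5 and 57% of those with platelets under 25 stayed in. With a weak assumed neutrophil fall, only 48% of those excluded had a low baseline.
- A reader might infer that the rule shrinks a between-arm difference in nadir depth by a known fraction. The SAP plans time to nadir in days and no comparison of depth. Any such fraction would also rest on assumed falls. For normally distributed log10 changes with SD 0.4, means of −0.6 and −0.8 would lose 17% of the difference, and means of −1.0 and −1.2 would lose 3%. Weaker falls would lose more, but both arms receive cytarabine, which Protocol 1.4 describes as a potent marrow suppressant.

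**Conclusion.** The point holds in limited form. Read as written, the exclusion makes entry to the time-to-nadir display depend on a post-randomization outcome. It forces the Kaplan-Meier curve to 100% in both arms and leaves this analysis unable to show whether falls are more frequent on one arm. That follows from the rule alone and needs no assumption about rates.

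The size is unknown. The tabulated differences of 5 to 15 points show what could be hidden under assumed rates and are not estimates. If nearly every patient in both arms has a fall, which is possible with cytarabine in both, few patients are removed and little is lost. No direction of bias in days to nadir can be stated from the documents.

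The consequence is confined to a descriptive safety output without a test. The overall survival analysis and its type I error are untouched. This is a minor improvement, worth making because it is almost free.

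**What to change.** Amend SAP 4.7.3 as follows.

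- In the Kaplan-Meier analysis of time to nadir, include all treated patients with at least one post-baseline Cycle 1 count. Censor those with no value below baseline at the end of the interval.
- Report by arm the number and percentage of these patients with no fall, ideally by baseline CTCAE grade.
- Label the boxplots and summary statistics in days as restricted to patients with a nadir, and reword the sentence that introduces them so that it agrees.
- Optionally, summarise the lowest post-baseline value in all treated patients with a post-baseline count, whether or not it is below baseline.

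The cost is SAP wording and minor programming. No new data are needed.
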